13.5 Efficacy Analyses

Efficacy analysis will be conducted on the FAS and PPS. The interpretation of results from statistical tests will be based on the FAS. The PPS will be used to assess the robustness of the results from the statistical tests based on the FAS.

Efficacy within certain subgroups of clinical interest (e.g., age, sex, race, and ethnicity) will be examined. Further details on the subgroups of interest will be specified in the SAP.

Change from baseline in average AM rTNSS and iTNSS over the first 6, 30, and 52 weeks of treatment will be analyzed using an analysis of covariance (ANCOVA) model adjusting for study treatment group, site, and baseline (defined as the average of the last 4 consecutive AM assessments during the last 4 days of the run-in period from the Day -3 AM assessment to the AM assessment on the day of randomization). At least 2 out of 4 assessments (scores) should be available in order to calculate the baseline scores for the AM rTNSS and iTNSS (linear, continuous covariate). Least squares means (LSMs) of the treatment differences and associated 95% confidence intervals (95% CIs) and p-values will be presented. A multiple, imputation-based approach where complete data sets are drawn will be used for handling missing data in the efficacy analysis. The imputation model will be defined and fully detailed in the SAP.

Changes from baseline in rTNSS and iTNSS at the end of each week of treatment and changes from baseline in individual nasal symptom scores over the first 6, 30, and 52 weeks (and at the end of each treatment week) of the treatment period will be analyzed in a similar manner as described above.

Changes from baseline in RQLQ(S) at Weeks 6, 30, and 52 will be analyzed for the FAS and the RQLQ(S) Analysis Set using ANCOVA models adjusting for study treatment group, site, and baseline RQLQ(S) (linear, continuous covariate). For subjects who withdraw early from the study, the RQLQ(S) score at their discontinuation visit will be used.

The analyses of RCAT results will be similar to the RQLQ(S) analyses except the RQLQ(S) analysis set will not apply.

Detailed statistical analyses and methods will be provided in the SAP.

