## 1.0 Changes to the Protocol Defined Statistical Analysis Plan

- The protocol states that the efficacy analysis will be conducted using an analysis of covariance (ANCOVA) model (adjusting for study treatment group, site and baseline). The efficacy analysis will now be analyzed using a mixed models repeated measures (MMRM) model. This will be more applicable to the design of the study, and assesses missing data using the Missing at Random (MAR) assumption. More detail is in Section [12.3](#).
- The protocol states that ‘A multiple, imputation-based approach where complete data sets are drawn will be used for handling missing data in the efficacy analysis.’ Because assessing efficacy is a secondary objective of the study, the sentence has been modified to state ‘A multiple, imputation-based approach *may* be considered for handling missing data for AM reflective Total Nasal Symptom Score (rTNSS) and AM instantaneous Total Nasal Symptom Score (iTNSS) upon review of amount of missing data observed’. More details in Section [12.3](#).
- The protocol states that the computer-generated randomization scheme will be reviewed and approved by an independent statistician and the randomization will be stratified by site. This was inaccurately stated. The computer-generated randomization scheme will be reviewed and approved by a statistician and the randomization will not be stratified by site. More detail is in Section [7.0](#).
- The protocol has defined the Full Analysis Set (FAS) as ‘The FAS will consist of all subjects who are randomized and received at least 1 dose of Investigational Product (IP) and have at least 1 post-baseline efficacy assessment.’ To add more clarity the definition of the FAS is ‘The FAS will consist of all subjects who are randomized and received at least 1 dose of IP and have at least 1 post-baseline AM rTNSS assessment.’

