#### 4.2 Secondary Endpoints

##### Efficacy Endpoints:

- Change from baseline in the average AM subject-reported rTNSS over the first 6, 30, and 52 weeks of treatment.
- Change from baseline in the average AM subject-reported instantaneous Total Nasal Symptom Score (iTNSS) over the first 6, 30, and 52 weeks of treatment.
- Change from baseline in the overall Rhinoconjunctivitis Quality of Life Questionnaire – Standardized Activities (RQLQ(S)) score at Weeks 6, 30, and 52 for the Full Analysis Set (FAS).

|  |                                    |                                  |
|--|------------------------------------|----------------------------------|
| Protocol Number:
GPL/CT/2014/018/III
(Study No. GSP 301-303) | SAP Version Number:
Version 1.0 | SAP Version Date:
04-Apr-2017 |
|--|------------------------------------|----------------------------------|

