## 8.0 Sample Size Determination

The sample size of 600 subjects for this study (400 subjects on GSP 301 NS and 100 subjects in each of the 2 placebo groups) is based on the ICH E1 Guideline (ICH E1) and the FDA Guidance on Allergic Rhinitis which requires treatment of at least 300 subjects for 6 months and 100 subjects for 1 year. Based on an estimated attrition rate of 25% after 6 months and 50% after 52 weeks, 400 subjects in the GSP 301 NS treatment group are considered sufficient to meet the above requirements.

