## STATISTICAL ANALYSIS PLAN

|  |                                    |                                  |
|--|------------------------------------|----------------------------------|
| Protocol Number:
GPL/CT/2014/018/III
(Study No. GSP 301-303) | SAP Version Number:
Version 1.0 | SAP Version Date:
04-Apr-2017 |
|--|------------------------------------|----------------------------------|

site-by-treatment and baseline-by-treatment will be investigated separately in the model and will only be included in final model if they are statistically significant at the  $\alpha=5\%$  level. An unstructured (UN) covariance will be assumed. If the model does not converge using the unstructured covariance structure, the autoregressive (order 1) AR(1) structure will be used. If this also does not converge other covariance structures deemed appropriate to fit the data will be used. This method will assume that any missing data is Missing at Random (MAR). The statements of a SAS PROC MIXED analysis would be (if the interactions of treatment\*baseline and treatment\*site is not statistically significant):

```
proc mixed;  
class subject treatment site week;  
model change = treatment site baseline week;  
repeated week / subject = subject type=UN;  
lsmeans treatment / cl diff e ;  
ods output lsmeans=lsmeans ;  
ods output diffs=diffs ;  
run ; quit ;
```

The adjusted means for each treatment and the estimated treatment differences for the treatment comparisons will be presented together with 95% confidence intervals for the differences and p-values for the treatment comparisons. The adjusted means and estimated treatment differences for the treatment comparisons will also be plotted, with corresponding 95% confidence intervals.

The responses for the first 6, 30 and 52 weeks of treatment will all be analysed in separate statistical models.

A multiple, imputation-based approach may be considered for handling missing data for AM rTNSS upon review of amount of missing data observed.

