**12.4.2.2 Change in the average AM subject-reported rTNSS and iTNSS from baseline to the end of each treatment week**

The efficacy endpoints rTNSS and iTNSS will be analyzed separately using a mixed model repeated measures model, adjusting for covariates that include treatment, site, baseline and week as the within-subject effect, and the model will include treatment\*week interaction term (for the FAS). The statements of a SAS PROC MIXED analysis would be:

```
proc mixed;
```

|  |                                    |                                  |
|--|------------------------------------|----------------------------------|
| Protocol Number:
GPL/CT/2014/018/III
(Study No. GSP 301-303) | SAP Version Number:
Version 1.0 | SAP Version Date:
04-Apr-2017 |
|--|------------------------------------|----------------------------------|

```
class subject treatment site week;
model change = treatment site baseline week treatment*week;
repeated week / subject = subject type=UN;
lsmeans treatment treatment*week / cl diff e ;
ods output lsmeans=lsmeans ;
ods output diffs=diffs ;
run ; quit ;
```

For each week, the adjusted means for each treatment and the estimated treatment differences for the treatment comparisons will be presented together with 95% confidence intervals for the differences and p-values for the treatment comparisons. The adjusted means and estimated treatment differences for the treatment comparisons will also be plotted, with corresponding 95% confidence intervals.

Descriptive statistics (number of subjects, mean, standard deviation, median, minimum and maximum) will be provided for baseline, post treatment and change from baseline by treatment group and week (for both the FAS and the PPS).

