LSMeans, Std Err of LSMeans, 95% confidence intervals and p-values are based on separate mixed model repeated measures models for each week assessment, with change from baseline as dependent variable, treatment group and site as fixed effect, baseline as covariate, and week as the within-subject effect.

Programming note: the interaction terms treatment\*baseline and treatment\*site will only be included in the footnote if significant in the model

Data source: xx

Created on: ddmmyy hh:mm

Page 1 of N

|  |                                    |                                  |
|--|------------------------------------|----------------------------------|
| Protocol Number:
GPL/CT/2014/018/III
(Study No. GSP 301-303) | SAP Version Number:
Version 1.0 | SAP Version Date:
04-Apr-2017 |
|--|------------------------------------|----------------------------------|

**T14.1.9.12.3 Summary of Average AM rTNSS  
(Per Protocol Set)**  
Repeat of Table T14.1.9.12.1 for Per Protocol Set

**T14.1.9.12.4 Summary of Repeated Measures Analysis Results in Average AM rTNSS over the First 6, 30, and 52 Weeks of Treatment  
(Per Protocol Set)**  
Repeat of Table T14.1.9.12.2 for Per Protocol Set

**T14.1.9.12.5 Subgroup Analyses (Age Group): Summary of Average AM rTNSS  
(Full Analysis Set)**  
Repeat of Table T14.1.9.12.1 for age group

**T14.1.9.12.6 Subgroup Analyses (Sex): Summary of Average AM rTNSS  
(Full Analysis Set)**  
Repeat of Table T14.1.9.12.1 for sex

**T14.1.9.12.7 Subgroup Analyses (Race): Summary of Average AM rTNSS  
(Full Analysis Set)**  
Repeat of Table T14.1.9.12.1 for race

**T14.1.9.12.8 Subgroup Analyses (Ethnicity): Summary of Average AM rTNSS  
(Full Analysis Set)**  
Repeat of Table T14.1.9.12.1 for ethnicity

|  |                                    |                                  |
|--|------------------------------------|----------------------------------|
| Protocol Number:
GPL/CT/2014/018/III
(Study No. GSP 301-303) | SAP Version Number:
Version 1.0 | SAP Version Date:
04-Apr-2017 |
|--|------------------------------------|----------------------------------|

**T14.1.9.13.1 Summary of Average AM iTNSS  
(Full Analysis Set)**

| Treatment Group                          | Week     | Observed Data |             |        |            | Change from Baseline |             |        |            |
|--|----------|---------------|-------------|--------|------------|----------------------|-------------|--------|------------|

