**T14.1.9.17.1 Summary of Repeated Measures Analysis Results in Average AM rTNSS over Each Treatment Week  
(Full Analysis Set)**

| Week    | Treatment Group                          | Number of Subjects (n) | LSMean | Std Err LSMean | Treatment vs. Placebo NS pH [REDACTED] |                    |               |         |
|---------|--|------------------------|--------|----------------|--|--------------------|---------------|---------|
|         |  |                        |        |                | LSMean Difference                      | Std Err Difference | 95% CI        | P-value |
| Week 1  | GSP 301 placebo NS pH [REDACTED] (N=xxx) | xxx                    | xxx.xx | xxx.xx         |  |                    |               |         |
|         | GSP 301 NS (N=xxx)                       | xxx                    | xxx.xx | xxx.xx         | xxx.xx                                 | xxx.xx             | xx.xx – xx.xx | x.xxxx  |
| etc     | GSP 301 placebo NS pH [REDACTED] (N=xxx) | xxx                    | xxx.xx | xxx.xx         |  |                    |               |         |
|         | GSP 301 NS (N=xxx)                       | xxx                    | xxx.xx | xxx.xx         | xxx.xx                                 | xxx.xx             | xx.xx – xx.xx | x.xxxx  |
| Week 52 | GSP 301 placebo NS pH [REDACTED] (N=xxx) | xxx                    | xxx.xx | xxx.xx         |  |                    |               |         |
|         | GSP 301 NS (N=xxx)                       | xxx                    | xxx.xx | xxx.xx         | xxx.xx                                 | xxx.xx             | xx.x – xx.x   | x.xxxx  |

Baseline is defined as the mean of the last 4 AM reading scores including the AM on the day of randomization

n: Number of subjects with data available in the specific treatment group

LSMeans: Least square means; Std Err LSMean: Standard error of the LSMean

LSMeans, Std Err of LSMean, 95% confidence intervals and p-values are based on mixed model repeated measures model with change from baseline as dependent variable, treatment group and site as fixed effect, baseline as covariate, week as the within-subject effect and week-by-treatment interaction.

Programming note: the interaction terms treatment\*baseline and treatment\*site will only be included in the footnote if significant in the model

Data source: xx

Created on: ddmmyy hh:mm

Page 1 of N

|  |                                    |                                  |

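### The 6-, 30- and 52-week symptom-score models omit treatment-by-week, so the reported difference is guaranteed to be the named period average only if the effect is constant over weeks

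*SAP*

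**What the plan says.** SAP 4.2 names the endpoint as "Change from baseline in the average AM subject-reported rTNSS over the first 6, 30, and 52 weeks of treatment", and likewise for iTNSS and the individual symptoms. Protocol 13.5 planned an ANCOVA with that period average as the response, and stated: "A multiple, imputation-based approach where complete data sets are drawn will be used for handling missing data in the efficacy analysis". On completed data every week then counts equally.

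SAP 1.0 replaces the ANCOVA with a repeated-measures model and gives as its reason: "This will be more applicable to the design of the study, and assesses missing data using the Missing at Random (MAR) assumption". It makes multiple imputation optional and does not mention how weeks are weighted.

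The response becomes the weekly mean (SAP 11.1). For rTNSS (12.3.2.1), iTNSS (12.3.2.2) and individual symptoms (12.4.2.1) the code is "model change = treatment site baseline week", fitted separately for each period, with one treatment LS-mean difference reported. The footnotes to T14.1.9.12.2, T14.1.9.13.2 and T14.1.9.15.2 agree, ending at "baseline as covariate, and week as the within-subject effect". For rTNSS and iTNSS, site and baseline interactions with treatment are tested for inclusion; the interaction with week is not considered. The covariance is unstructured, then AR(1) if the fit fails, then another structure.

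The SAP does use treatment-by-week for RQLQ(S) (12.3.2.3) and for the end-of-week analyses (12.4.2.2, 12.4.2.3), where the request is "lsmeans treatment treatment*week / cl diff e".

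**The concern.** A model with week effects and one treatment coefficient assumes a common effect across weeks. If the effect is not common, generalised least squares still returns one number, but it is a weighted mean of the weekly effects. The weights come from the correlation structure and the dropout pattern, not from the 1/6, 1/30 or 1/52 that an average over the period implies. The estimate, CI and p-value would then describe a quantity other than the one in the endpoint's name. The weights would also depend on which covariance structure happened to converge. An unstructured matrix has 21, 465 and 1,378 parameters for 6, 30 and 52 weeks (T(T+1)/2), so the three periods need not end up with the same structure.

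**Working it through.** **Plan's own figure.** SAP 8.0 states: "Based on an estimated attrition rate of 25% after 6 months and 50% after 52 weeks". Then 300/(1 − 0.25) = 400 and 100/(1 − 0.50) = 200. The larger is 400, and 4:1:1 gives 600. This reproduces; it is used here only as the source of the attrition.

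**Formula.** Let e be the vector of weekly effects, V the within-subject covariance of the weekly means, and f the share of subjects in each dropout pattern, taken as equal in both arms. With I = Σ f·V⁻¹ over patterns, the expected coefficient is w′e, where w = I1/(1′I1). The named average is mean(e). The gap is w′e/mean(e) − 1. The weights sum to 1, so a constant effect gives a gap of zero for any V and any such dropout.

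**A case that can be checked by hand.** Under AR(1) with complete data, each end week has weight 1/[2 + (T − 2)(1 − ρ)] and each inner week (1 − ρ) times that.
- T = 6, ρ = 0.9: the denominator is 2 + 4 × 0.1 = 2.4, so end weeks get 0.417 and inner weeks 0.042 (equal share 0.167).
- Assume the effect reaches 25, 50, 75 and then 100% from Week 4. The mean is 4.5/6 = 0.750.
- The model gives 0.417 × 1.25 + 0.042 × 3.25 = 0.656, a gap of −12.5%.
- At ρ = 0.8 the denominator is 2.8, the model gives 0.679 and the gap is −9.5%.

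**Scenarios.** The documents give no SD, correlation or effect profile for this trial, so all of these are assumed. V has constant SD and is either AR(1) or a subject effect (ICC 0.5) plus AR(1), with ρ of 0.8 and 0.9. The share observed at week t is 1 − 0.5t/52, which gives 25% lost at Week 26 and 50% at Week 52.

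| Period and data | Assumed profile | Gap |
|---|---|---|
| any | constant | 0 |
| 6 weeks, complete | Week 1 at 80% or 90%, then full | −1.9 to −5.2% |
| 6 weeks, complete | full effect reached at Week 4 | −9.5 to −12.5% |
| 30 weeks, attrition | 90% in Week 1, full to Week 6, then 70% | +2.4 to +3.9% |
| 30 weeks, attrition | rising linearly, 50% at Week 1 to 100% at Week 52 | about −2 to −3% |
| 52 weeks, attrition | 90% in Week 1, full to Week 6, then 70% | +2.8 to +5.1% |
| 52 weeks, attrition | rising linearly as above | −4.6 to −7.3% |
| 52 weeks, attrition | full to Week 6, then half | +8.8 to +16.5% |

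- Compound symmetry (ICC 0.6) gives zero with complete data. At 52 weeks with attrition it gives +4.2% (falling to 70%) and −8.0% (rising linearly).
- With complete data, the mild 30- and 52-week gaps shrink to +1.2 to +2.4% for the fall to 70%, and to zero for the linear rise.
- At 52 weeks with attrition, Weeks 1–6 carry 21.4–29.9% of the weight, against 6/52 = 11.5%.
- If SD also rises from 1.7 to 2.2 over Weeks 1–8, even the mild profiles reach −15% at 6 weeks and +16% or −19% at 52 weeks.

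**Precision.** The SE of the equal-week contrast relative to the planned one is [√(1′I⁻¹1)/T]/√[1/(1′I1)]. It is 0.4–5.9% larger with constant SD and 4–14% larger with the rising SD.

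**Scale only.** Protocol 5.4 gives a Phase 2 rTNSS difference of −1.1703 with 97.5% limits −1.7315 and −0.6090, so SE = (1.7315 − 0.6090)/(2 × 2.2414) = 0.250. Then 2–8% of 1.1703 is 0.02–0.09 points (0.1–0.4 SE), and 9–17% is 0.11–0.20 points (0.4–0.8 SE). That trial was in seasonal disease with a different design.

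**The case against.** The best defence has four parts.

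- **The plan is explicit.** Protocol 13 lets the SAP supersede the protocol, SAP 1.0 discloses the change of model, and code and footnotes agree. That makes the analysis reproducible. It does not make the coefficient the stated average.
- **A changing effect would be seen.** T14.1.9.17.1, T14.1.9.17.2, T14.1.9.18.1 and T14.1.9.18.2 report weekly differences with CIs and p-values from models with "week as the within-subject effect and week-by-treatment interaction", and F15.4.1 and F15.4.2 plot the differences for rTNSS and iTNSS. A reader could average the first 6, 30 or 52 rows. The code in 12.4.2.2 and 12.4.2.3 even requests an equal-week 52-week mean. This is real mitigation. However, the shells carry weekly rows only. A period CI or p-value cannot be rebuilt from them without the covariances between weeks, and no rule names the average as the period estimate.
- **The common-effect model is more precise**, and equal weighting asks more of missing at random in late weeks, where half the subjects are expected to be gone. Both points stand as costs of the fix.
- **The stakes are low.** Efficacy is the secondary objective, SAP 6.0 states no hypotheses, and if there is no effect in any week every weighting gives zero. This also stands.

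A reader might go further and infer that the effect will change, so that the estimate is biased in a known direction. The documents do not support that. Protocol 5.2 describes onset over hours to days for intranasal corticosteroids in general. Protocol 5.6 has olopatadine acting within 30 minutes. The rescue start at Day 43 (Protocol 9.6) gives timing, not use by arm.

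**Conclusion.** The point holds as a mismatch between the named endpoint and the planned contrast in all three sets of period models. Constancy over weeks is sufficient for equality, not strictly necessary: compound symmetry with complete data, or AR(1) with complete data and a linear trend, also balances. The planned covariance sequence and expected attrition do not secure those cases.

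Confidence is high on the omission and low on its size. Both illustrative ranges rest on assumed correlations, SDs and profiles, on linear attrition equal in both arms, and on dropout unrelated to outcome. A reader might take 2–8% or 9–17% as the likely error or as a ceiling; it is neither, because size and sign depend on the profile chosen and a changing SD widens the gap. Primary safety results and the sample size are unaffected. The correction is worth making because it is small and aligns the estimate, CI and p-value with the endpoint.

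**What to change.** Add treatment*week to the model statements in SAP 12.3.2.1, 12.3.2.2 and 12.4.2.1. Keep the treatment LS-mean request, which then averages weeks equally, and name that difference, with its 95% CI and p-value, as the period estimate. Update the footnotes to T14.1.9.12.2, T14.1.9.13.2 and T14.1.9.15.2 and to the tables that repeat them. If the present weighting is intended, say so and reword the endpoint.

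The cost is one model term already coded in 12.4.2.2, some text, an SE about 0.4–6% larger with constant SD (more if SD changes over weeks), and heavier reliance on missing at random in late weeks.

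The cross-reference in 12.4.2.4 to a section without the interaction, while the PNSS, RQLQ(S) and RCAT shells include it, is a separate defect. It should be raised on its own and adds no weight here.

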## 7.0 Randomization and Blinding

Subjects will be assigned to 1 of the 3 treatment groups in a 4:1:1 ratio based on a computer-generated randomization scheme that will be reviewed and approved by a statistician.

This study is designed as a double-blind study. The blinding will be maintained by packaging the active products and placebo in identical bottles and outer cartons. Additionally, an unblinded qualified person who is not associated with the study team, will facilitate the randomization process to ensure that the double-blind design of the study is maintained.

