### Derivation Method and Baseline

#### Mixed Model Repeated Measures (MMRM) Approach

Change from baseline in average AM rTNSS to the end of each treatment week will be derived as the average of post-baseline AM rTNSS scores by week (i.e average AM rTNSS score for Week 1 is calculated as the mean rTNSS score in Week 1), where baseline is defined as the average of the last 4 consecutive AM assessments during the last 4 days of the run-in period from the Day -3 AM assessment to the AM assessment on the day of randomization. At least 2 out of 4 assessments (scores) should be available in order to

|   |   |   |
|---|---|---|
|  | STATISTICAL ANALYSIS PLAN          |   |
| Protocol Number:
GPL/CT/2014/018/III
(Study No. GSP 301-303)         | SAP Version Number:
Version 1.0 | SAP Version Date:
04-Apr-2017 |

calculate the baseline scores for the AM rTNSS. In order to calculate the average of post-baseline AM rTNSS scores by week, at least 2 scores need to be present.

The same derivation method will also be applied to all other nasal symptom efficacy endpoints.

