### 12.3 Efficacy Analyses of Efficacy Endpoints

For all efficacy statistical analysis of efficacy endpoints, the comparison of interest will be GSP 301 NS vs. placebo NS pH [REDACTED]. The statistical analysis will only include up to week 52 data in the analysis.

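### If the 52-week unstructured fit converges, the SAP's pooled-effect PROC MIXED code prints 95% intervals about 9% too narrow, and a nominal 5% test runs at about 7.3% to 7.5% or somewhat more

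*SAP*

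**What the plan says.** SAP 11.1 makes the unit of analysis a weekly mean: "the average of post-baseline AM rTNSS scores by week". SAP 12.3.2.1 then specifies, for rTNSS, "model change = treatment site baseline week" together with "repeated week / subject = subject type=UN", and the text adds: "An unstructured (UN) covariance will be assumed". There is no treatment-by-week term, so the model estimates one treatment effect across all weeks. The three periods are kept apart: "The responses for the first 6, 30 and 52 weeks of treatment will all be analysed in separate statistical models". The matrix therefore has 6, 30 or 52 levels.

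The same code appears in 12.3.2.2 (iTNSS) and 12.4.2.1 (the four individual symptoms, reflective and instantaneous). No `ddfm=` or `EMPIRICAL` option is given, and the SAP names neither Kenward-Roger, Satterthwaite nor sandwich standard errors. If the unstructured fit fails, the SAP moves to AR(1), then to another structure judged suitable. Each comparison is reported with a 95% interval and a p-value. Under SAP 12.3, "the comparison of interest will be GSP 301 NS vs. placebo NS pH" (the rest of that label is redacted).

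**The concern.** With an unstructured matrix and a single pooled effect, the model weights the 52 weekly differences using weights estimated from the same data. For complete data this is equivalent to an ANCOVA on one summary of the weekly scores, with the other 51 contrasts among weeks as estimated covariates. The default model-based standard error ignores both the degrees of freedom those covariates use and the noise in the weights. The usual reassurance, that this hardly matters with 100 or more subjects per arm, holds when the number of repeated levels is small. Fifty-one estimated covariates are not small against roughly 550 error degrees of freedom.

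At stake is the stated coverage of the 52-week intervals for rTNSS, iTNSS and eight symptom scores: ten comparisons in the FAS, plus rTNSS and iTNSS again in the PPS. The protocol's ANCOVA on each subject's average (13.5) does not estimate such weights. The feature arrived when SAP 1.0 replaced ANCOVA with MMRM.

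**Working it through.** **Inputs from the documents**

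- SAP 8.0: "400 subjects on GSP 301 NS and 100 subjects in each of the 2 placebo groups", so N = 400 + 100 + 100 = 600. Allocation (SAP 7.0): "Subjects will be assigned to 1 of the 3 treatment groups in a 4:1:1 ratio".
- Attrition (SAP 8.0): 25% after 6 months, 50% after 52 weeks.
- Repeated levels p = 6, 30 and 52.

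**Assumptions**

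- 40 sites, range 1 to 60; the number is not given.
- All three arms are in the model. The results shells show only two, so two arms are a sensitivity case.
- For the attrition runs: the correlation over weeks, and dropout completely at random.

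**The plan's own figure.** 300 / (1 − 0.25) = 400 and 100 / (1 − 0.50) = 200, so 400 on active treatment meets both exposure targets. The documents state no efficacy power and no type I error for the MMRM, so there is nothing further to reproduce.

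**Covariance parameters**, p(p + 1)/2: 6 weeks, 6 × 7/2 = 21; 30 weeks, 30 × 31/2 = 465; 52 weeks, 52 × 53/2 = 1,378.

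**Complete data, exact result.** Let k = p − 1, and let v be N minus the rank of intercept, treatment, site and baseline. With 40 sites, v = 600 − 1 − 2 − 39 − 1 = 557.

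- Printed variance / true variance = [(v − k)/v] × [(v − k − 1)/(v − 1)].
- The SE ratio is its square root.
- Actual level = 2 × P(Z > t × SE ratio), where t is the 0.975 quantile on v degrees of freedom (1.964 here).

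| Model | k | Variance ratio | SE ratio, printed/true | Actual level |
|---|---|---|---|---|
| 6 weeks | 5 | (552/557)(551/556) = 0.982 | 0.991 | 5.2% |
| 30 weeks | 29 | (528/557)(527/556) = 0.898 | 0.948 | 6.3% |
| 52 weeks | 51 | (506/557)(505/556) = 0.825 | 0.908 | 7.4% |

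At 52 weeks, 1/0.908 = 1.10. The valid interval is about 10% wider than the printed one, so the printed one is about 9% too narrow. Moving from 1 to 60 sites changes the ratio from 0.914 to 0.905 and the level from 7.25% to 7.55%. The within-subject correlation does not enter the complete-data result.

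**Simulation under the null, 52 weeks, 40 sites, SAP model fitted by REML**

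| Data | SE ratio | Level (Monte Carlo SE) |
|---|---|---|
| Complete | 0.913 | 7.3% (0.4) |
| Attrition; subject effect + AR(0.85) + noise, two runs | 0.900, 0.897 | 7.5% (0.4), 8.2% (0.3) |
| Attrition; compound symmetry 0.6 | 0.906 | 7.6% (0.5) |
| Attrition; AR(0.95) | 0.882 | 8.4% (0.5) |

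A separate simulation without site or baseline terms gave 7.4% (Monte Carlo SE 0.7) under the planned attrition. If only the two compared arms are modelled (N = 500), the complete-data level is 8.1%, and a run with attrition gives 8.7% (0.7).

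**Effect of coarser time levels.** Thirteen 4-week blocks need 13 × 14/2 = 91 parameters. With k = 12, the variance ratio is (545/557)(544/556) = 0.957, the SE ratio 0.978 and the level 5.5%. The separate simulation gave a true/printed ratio of 1.02 and 5.3% with default standard errors. Five 6-week blocks need 15 parameters. With k = 4, (553/557)(552/556) = 0.986, giving an SE ratio of 0.993 and a level of 5.1%.

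**AR(1) fallback with model-based standard errors.** If the truth is AR(0.95), the SE ratio is 1.00 and the level 5.0%. If subjects carry a persistent effect, the ratio is 0.51 (level about 32%) under the mixed structure and 0.35 (about 50%) under compound symmetry.

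**The case against.** The strongest reply is that the figures are conditional. The SAP has a fallback, and a 1,378-parameter fit may not converge; under AR(1) the numbers in the first two tables do not apply. That stands. It does not rescue the analysis, because the fallback may be exact or far worse depending on a correlation nobody yet knows, and Kenward-Roger would not repair a wrong structure.

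A second reply is that the consequence is small. A 10% wider standard error moves the critical value to 1.96 × 1.10 = 2.156, so only printed p-values between about 0.031 and 0.05 would change sides. Efficacy is a secondary objective, SAP 6.0 gives hypotheses as not applicable, and the 5% level is implied by the 95% intervals rather than set. This also stands, and it limits the severity.

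A reader might infer that every mixed model in the SAP is affected and needs `ddfm=kr`. The documents do not support that. RQLQ(S) (12.3.2.3) has three visits, hence six covariance parameters, and a week-by-treatment term. The by-week models (12.4.2.2, 12.4.2.3) also carry treatment-by-week and were not part of these calculations. With 52 weekly levels, Kenward-Roger may not be practical to compute there.

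**Conclusion.** The point holds as a conditional statement about the pooled 52-week models, with a modest counterpart at 30 weeks (about 6%) and nothing of note at 6 weeks. This is executable code with a determinate output, so it is an error in the plan as written and not merely an unstated detail.

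The complete-data size rests only on N, p and an assumed site count, to which it is insensitive. The attrition range also rests on the assumed correlation structures and on dropout completely at random. Kenward-Roger itself was not simulated; the block-mean reduction was.

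A reader might take this to mean that the trial's main conclusions lose error control. They do not: the primary endpoints are safety, and none uses this model. The change is worth making before unblinding but is not critical.

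**What to change.** Limit the change to the pooled 30- and 52-week models in SAP 12.3.2.1, 12.3.2.2 and 12.4.2.1.

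1. Enter block means as the repeated measure, for example five 6-week blocks for 30 weeks and thirteen 4-week blocks for 52 weeks. State the minimum number of observed weeks for a block to count, since SAP 11.1 sets a minimum only for weekly means.
2. Add `ddfm=kr` to those MODEL statements.
3. Pre-specify empirical (sandwich) standard errors for AR(1) or any other structured fallback.

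On this evidence the 6-week, RQLQ(S) and by-week models can stay as they are. The cost is a derived block variable, a rule for partly observed blocks, two code options and slightly wider intervals. The smaller matrix should also make the fallback less likely to be needed.
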